#### Interim Analysis.

Once the first 6 patients are recruited, the study recruitment will be temporarily suspended and the patients will be followed for 3 months to monitor any toxicity issues. At the end of 3 months follow-up of the 6 patients, the results will be sent to the DSMB for further evaluation. The trial will be terminated if grade 3 or more toxicity is observed in more than 2 patients or at least one showing grade 4 level toxicity. Otherwise, upon approval from the DSMB, the second phase of recruiting will be initiated.

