#### 5.0 STATISTICAL CONSIDERATIONS

A maximum of 20 patients will be enrolled into the study. The accrual rate is expected to be 1-2 patients per month based on the volume of patients with stage 2-3 HS treated within the Montefiore Hidradenitis Suppurativa Treatment Center. An early stopping rule for safety will be implemented as follows based on Simon's optimal two-stage design. After the first 6 patients have been enrolled, accrual will be temporarily suspended while these patients are monitored for occurrence of treatment-related grade ≥ 3 toxicity for 3 months. At the end of 3

months, results will be sent to the DSMB for further evaluation. The trial will be terminated early if more than 1 patient experiences grade  $\geq$  3 treatment related toxicity or any patient experiences grade 4 toxicity. Otherwise, upon approval from the DSMB, the second phase of recruiting will be initiated. If 1 or fewer grade  $\geq$  3 toxicities and 0 grade 4 toxicities are observed, the trial will continue until a total of 20 patients have been evaluated. At the end of the trial, the treatment will be considered safe and worthy of further study if no more than 3 patients experience grade  $\geq$  3 treatment related toxicity and none experience grade 4 treatment related toxicity.

The target Grade  $\geq$  3 toxicity rates is no more than 10%, and a toxicity rate greater than 30% is considered clinically unacceptable. The design specified above has the following operating characteristics. The probability of accepting the treatment for further study if the toxicity rate is unacceptably high (> 30%) is at most 10%. In contrast, there is an 80% probability of accepting the treatment for further study if the toxicity rate is less than 10%. In addition, if 0 out of 20 patients experience Grade 4 toxicity at the end of the study, we will be able to conclude with 95% confidence that the true Grade 4 toxicity rate is not greater than 17%.

The proportion of patients who have treatment-related toxicity will be computed, along with exact 95% confidence intervals. Since the study is a phase I trial, we will NOT do any hypothesis testing or models, The study will present the descriptive summary statistics for each outcomes. Biomarker levels measured at different time points and other continuous variables will be summarized by computing means, medians, standard deviations and ranges.

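### With no Grade 4 event in 20 patients, should the 95% upper bound be 13.9% rather than the stated 17%?

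*Combined protocol and SAP*

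**What the plan says.** The figure is in Section 5.0 (Statistical Considerations), at the end of the paragraph on operating characteristics. The condition is "if 0 out of 20 patients experience Grade 4 toxicity at the end of the study", and the conclusion drawn is "we will be able to conclude with 95% confidence that the true Grade 4 toxicity rate is not greater than 17" percent. The sentence does not say whether the bound is one-sided or two-sided.

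The next paragraph of Section 5.0 gives the reporting method: "The proportion of patients who have treatment-related toxicity will be computed, along with exact 95% confidence intervals". It does not state sidedness either.

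Grade 4 toxicity is governed separately, by zero-event rules. The final criterion in Section 5.0 requires that "none experience grade 4 treatment related toxicity". The Interim Analysis text under Section 4.1 ends the trial on "at least one showing grade 4 level toxicity", and Section 5.0 has a matching stage 1 rule. None of these rules refers to 17%.

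**The concern.** A claim that a rate does not exceed some value concerns one direction only. A statistician who checks such a claim at 95% for zero events in n patients will normally solve (1 − p)^n = 0.05. For n = 20 that gives 13.9%, not 17%. Conversely, if the true rate were 17%, 20 event-free patients would occur with probability 2.4% rather than 5%. The stated confidence level and the stated bound therefore seem to come from different calculations.

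Safety is the primary objective, and this is the plan's only precision figure for Grade 4 toxicity. A wrong bound here would misinform the DSMB and readers about what 20 patients can rule out. It could also suggest that other figures in the section had not been checked.

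**Working it through.** **Inputs, all from Section 5.0:** n = 20 ("A maximum of 20 patients will be enrolled into the study"), x = 0 Grade 4 events, confidence level 95%, stated bound 17%, exact intervals for toxicity proportions. Two-sidedness of those intervals is an assumption, being the usual reading of a 95% confidence interval.

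**1. Reproducing the plan's figure.** For x = 0 the lower exact (Clopper-Pearson) limit is 0. The upper limit solves (1 − p)^n = α/2:

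1 − 0.025^(1/20) = 0.1684, or 16.8%, which rounds to 17%.

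The stated figure reproduces.

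**2. The one-sided alternative.** Putting all 5% in the upper tail:

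1 − 0.05^(1/20) = 0.1391, or 13.9%.

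The difference is 16.8 − 13.9 = 2.9 percentage points, or 3.1 from the rounded 17%.

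**3. Could 17% come from another method?** Upper limits for 0/20:

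| Method | Upper limit |
|---|---|
| Exact, two-sided 95% | 16.8% |
| Exact, one-sided 95% | 13.9% |
| Rule of three (3/20) | 15.0% |
| Wilson, two-sided | 16.1% |
| Wilson, one-sided | 11.9% |
| Agresti-Coull, two-sided | 19.0% |
| Jeffreys, two-sided | 11.7% |
| Jeffreys, one-sided | 9.0% |

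Of these, only the two-sided exact limit rounds to 17%. It is also the method that the next paragraph of the plan names.

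**4. Is the sentence true as worded?** The one-directional confidence attached to a bound p after 0/20 is 1 − (1 − p)^20.

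- At 17%: 1 − 0.83^20 = 1 − 0.0241 = 0.9759, or 97.6%.
- At 16.84%: 1 − 0.8316^20 = 0.9750, or 97.5%. The extra 0.1 point comes from rounding up to 17%.

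Both exceed 95%. A bound that holds with at least 97.5% confidence also holds with 95% confidence, so the sentence claims no more than the data would support.

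**5. Does the two-stage design upset the bound?** The event in question is reaching 20 patients with no Grade 4 toxicity. Its probability is (1 − p)^20 multiplied by the probability of passing stage 1 on the Grade 3 count, so it cannot exceed (1 − p)^20. At p = 17% it is at most 0.0241, whatever the Grade 3 boundary. Sections 4.1 and 5.0 give different stage 1 boundaries for Grade ≥3 events (more than 2 and more than 1 patients). They must be reconciled, but that is a separate matter and does not affect this bound.

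**6. Does anything depend on 17%?** The Grade 4 rules are zero-event rules. The 20 patients come from a two-stage design on Grade ≥3 toxicity, with 10% as the target rate and 30% as unacceptable. Replacing 17% by 13.9% would leave every boundary, error rate and sample size as it is.

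**The case for a change.** The strongest case on the other side is about clarity. The Grade 4 sentence mentions no interval, and the paragraph that does mention intervals does not state sidedness. A careful reader who applies the one-sided formula gets 13.9% and cannot tell from that sentence alone whether 17% is an error or a convention. Read literally at 95%, the sentence also undersells the data: a one-sided 95% bound no higher than 17% needs only 17 event-free patients (0/17 gives 16.2%, 0/16 gives 17.1%), not 20.

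The arithmetic is right, and it is fair to say that the convention is unlabelled. This still falls short of an error. The method is named in the adjacent paragraph, and its usual form returns the stated number. The 17-patient comparison has no bearing on the design, because the sample size was not chosen for Grade 4 precision.

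Replacing 17% by 14% could also introduce an inconsistency. The trial would still report an exact interval with an upper limit of 16.8% for the same 0/20 result, and the plan would quote a less cautious safety bound than its own report.

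**Conclusion.** The concern does not hold. The 17% is the upper limit of the exact two-sided 95% interval for 0/20 (16.8%, rounded), and the sentence is true and conservative as written, with 97.6% one-directional confidence where 95% is claimed. The one-sided bound of 13.9% is an equally legitimate way to describe the same result, and choosing between the two is a matter of preference. The difference is about 3 percentage points, in the cautious direction, and no decision, error rate or sample size changes with it.

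The reproduction rests on two assumptions: that the exact 95% intervals planned in Section 5.0 are two-sided, and that they extend to the Grade 4 proportion as a subset of treatment-related toxicity. The truth of the sentence rests on neither, since 1 − 0.83^20 exceeds 0.95 under any labelling. All that remains is an optional label on a correct figure that no rule uses.

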# 4.3 Study Endpoints

The primary endpoint of this study is safety, defined as the absence of any treatment-related Grade ≥3 adverse events during radiotherapy or within 3 months of radiotherapy completion, scored using CTCAE version 4.0.[6] Secondary study endpoints include:

# Optional

- Quality of Life
  - Improvement in NIH Patient-Reported Outcomes Measurement Information System (PROMIS) measures, including pain interference and physical functioning at 3 months (and optionally at 6 months and 12 months) after treatment[7, 8]
    - A one point change, either positive (improvement) or negative (decline), will be considered to be clinically meaningful[9]
- Inflammation as measured by ultrasound.
  - Noninvasive imaging, such as ultrasound (US), allows for an objective assessment of subclinical disease activity.
  - Anechoic area will be measured in the dermis before and after treatment, as well as other sonographic criteria of HS [10](See Appendix for Sonographic Scoring and Diagnosis of HS)
  - As there are no validated ultrasound criteria to measure clinical improvement, reduction in anechoic areas and sonographic criteria will be calculated. It is estimated that the treatment will induce a 50% reduction in the anechoic area.
  - Anechoic areas and other sonographic criteria will be correlated with PROMIS scores and Hurley Staging.
- Evaluation of cutaneous discharge
  - Swabs will be collected from discharge and sent for fluid count, which will include evaluation of infiltrating leukocytes from the discharge.
- Immunohistochemical Evaluation of HS Tissue Biopsies
  - Tissue biopsies will be collected before and after treatment. Tissue sections will be evaluated by H&E as well as immunohistochemistry for infiltrating leukocytes and other cells, such as T cells, B cells, plasma cells, dendritic cells, macrophages, and keratin. Image J will be used to quantify cells in a standard manner for comparison before and after treatment.

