PROMIS scores will be calculated using "PROMIS scoring manuals" found at http://www.healthmeasures.net/promis-scoring-manuals. The formula for scoring is: (Raw Sum of all questions answered X number of items on the short form) / Number of items that were actually answered. Using the provided score conversion table, the pro-rated raw score will be converted into a T-score for each participant.

Interpretation of PROMIS scores will be completed as explained at http://www.healthmeasures.net/score-and-interpret/interpret-scores/promis. T scores for each participant will be compared to calibrated scores of a validated reference population, where a score of 50 is the average for the United States general population with a standard deviation of 10.

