# **Appendix D: PROMIS- Physical Functioning**

#### PROMIS SF v1.0 - Physical Function 12a

#### **Physical Function – Short Form**

#### Please respond to each item by marking one box per row.

stand an "Suppo walking people.	lowing questions ask about your ability to nd move with and without support. rt" means using items such as canes, g sticks walkers and leg braces, or other	Yes	No	)			
PF Screencr 2	Can you walk 25 feet on a level surface (with or without support)?			J			
			articipant re articipant sl		tems o PFB5 and	proceeds	o PFA55
			Without any difficulty	With a little difficulty	With some difficulty	With much difficulty	Unable to
PFC8	Are you able to walk a block on flat grou	ınd?	5	4	3	2	1
PFC20	Are you able to walk up and down two st	to walk up and down two steps?		4	3	2	
PFA39	Are you able to run at a fast pace for two	ou able to run at a fast pace for two miles?		□ 4	3	2	
PFA25	Are you able to do yard work like raking weeding, or pushing a lawn mower?	leaves,	5	4	3	2	
			Not at all	Very little	Somewhat	Quite a lot	Cannot do
PF87	Does your health now limit you in doing strenuous activities such as backpacking, playing tennis, bicycling or jogging?	skiing,	5	4	3	2	I I
PFB5	Does your health now limit you in hiking couple of miles on uneven surfaces, inclubills?		5		☐ 3	2	
			Without any difficulty	With a little difficulty	With some difficulty	With much difficulty	Unable to do
PFA55	Are you able to wash and dry your body:	,	5	4	3	2	
PFCSS	Are you able to get in and out of bed?		□ .s	4	3	2	
PFA9	Are you able to bend down and pick up of from the floor?	lothing	s				

Investigator Format © 2008-2012 PROMIS Health Organization and PROMIS Cooperative Group

Page 1 of 2

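### The PROMIS pro-rating rule makes no exception for Physical Function items skipped because a patient cannot walk, so those items are scored as if done as well as the items answered

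*Combined protocol and SAP*

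**What the plan says.** Section 5.0 refers to online PROMIS scoring manuals and then writes out one rule for all PROMIS forms: "Raw Sum of all questions answered X number of items on the short form) / Number of items that were actually answered". It continues that "the pro-rated raw score will be converted into a T-score for each participant". It does not separate items a patient happened to leave blank from items the form told the patient to skip, and it sets no minimum number of answered items.

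Appendix D reproduces "PROMIS SF v1.0 - Physical Function 12a". The form starts with a Yes/No screener: "Can you walk 25 feet on a level surface (with or without support". The routing line beside it is damaged, but the fragment "o PFB5 and proceeds" is legible and is followed by PFA55 as the point where the form resumes. Six scored items are printed between the screener and PFA55: PFC8, PFC20, PFA39, PFA25, the item printed as PF87, and PFB5. The other six start at PFA55.

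Section 4.3 makes PROMIS measures, "including pain interference and physical functioning at 3 months", a secondary endpoint and adds: "A one point change, either positive (improvement) or negative (decline), will be considered to be clinically meaningful".

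**The concern.** Pro-rating is person-mean imputation: each unanswered item receives the mean of the items that were answered. That is reasonable when an item is blank for reasons unrelated to its likely answer. Here the items are unanswered because the patient has just reported being unable to walk a short distance, and the block covers walking a block, steps, running, yard work, strenuous activity and hiking. The rule fills them with the patient's average on items such as washing, getting out of bed, bending and reaching.

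The patients with the worst mobility are therefore scored too high. If the screener answer changes between visits, the change score is distorted and can have the wrong sign. With at most 20 patients and descriptive summaries only, one such patient would be visible in the results.

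**Working it through.** **Inputs from the documents.** Pro-rating formula (Section 5.0); 12 scored items, each scored 1 to 5 with higher meaning better function (Appendix D); maximum of 20 patients (Section 5.0). The plan states no numerical result on this point, so there is no figure to reproduce.

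**Inputs inferred or assumed.** That *No* skips all six items before PFA55 is inferred from the damaged routing line and the item order. The item sums below are illustrative.

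**Notation.** W is the sum of the six skippable items and S the sum of the other six. Each lies between 6 and 30.

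**1. Score at one visit.**
- All items answered: (W + S) × 12/12 = W + S, as it should be.
- Six items skipped, formula as written: S × 12/6 = 2S.
- Six items skipped and scored 1 each: S + 6.
- Excess of the written formula: 2S − (S + 6) = S − 6. For S = 6, 12, 18, 24, 30 this is 0, 6, 12, 18, 24 raw points. It is never negative.

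**2. Screener changes from *Yes* to *No*, S unchanged.** The change is 2S − (W + S) = S − W, so the score rises whenever S > W.
- W = 8, S = 21: before, 8 + 21 = 29. After, 2 × 21 = 42, a rise of 13. With skipped items scored 1: 21 + 6 = 27, a fall of 2.
- W = 8, S = 19: before, 27. After, 38, a rise of 11. With skipped items scored 1: 25, a fall of 2.

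**3. Same change, but S also worsens.** The score rises if 2 × (later S) > W + (earlier S).
- W = 8, S from 19 to 14: 27 to 28, still a rise.
- W = 8, S from 21 to 14: 29 to 28, no rise.

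**4. Screener changes from *No* to *Yes*, S unchanged.** Reversing the first example gives 42 to 29, a recorded fall of 13. With skipped items scored 1 it is 27 to 29, a gain of 2.

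**5. *No* at both visits.** The written formula gives a change of 2 × (later S − earlier S); lowest-category scoring gives (later S − earlier S). The direction is the same and the size is doubled.

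**6. Sensitivity to the damaged text.** Take the six skippable items as 2, 2, 1, 1, 1, 1 (W = 8) with S = 19, and skip k items counting back from PFB5:

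| k skipped | Pro-rated raw score (27 if all answered) |
|---|---|
| 1 | 26 × 12/11 = 28.4 |
| 2 | 25 × 12/10 = 30.0 |
| 3 | 24 × 12/9 = 32.0 |
| 4 | 23 × 12/8 = 34.5 |
| 5 | 21 × 12/7 = 36.0 |
| 6 | 19 × 12/6 = 38.0 |

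In this example the direction does not depend on the exact length of the skip.

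**7. Group mean.** In the first example of step 2 the two scoring rules differ by 42 − 27 = 15 raw points. One such patient in 20 moves the mean raw change by 15/20 = 0.75 raw points.

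**The case against.** The strongest objection is that Section 5.0 defers to a scoring manual that is not in the documents and may already say how a *No* answer is scored. That is possible, and it is why the fix includes checking the manual. It does not repair the protocol: the formula is written out without exception, and Section 6.2 requires the study to be run as the protocol describes.

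A second objection is that the documents do not say skipped items score 1. That stands as a matter of text. However, a patient who cannot walk 25 feet would be expected to answer *unable* on the harder walking items, so the lowest category is sound for those and reasonable for the rest of the block.

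A third is that the answered items are not all easy: they include opening a heavy door and a full day of manual labor. This stands. It makes the top of the range (S = 30, pro-rated to 60 out of 60) implausible for someone who cannot walk 25 feet, so 24 points is an arithmetic bound and should not be read as a typical error.

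A reader might also infer that the rule reverses the direction of the quality-of-life endpoint, or that one patient uses up most of the one-point threshold. The documents support neither. Reversal needs a changed screener answer and a sufficiently high S, as steps 2, 3 and 5 show. The 0.75 is in raw points, the plan converts to T-scores, and Section 4.3 does not state the scale of its one-point threshold. The Pain Interference form and the DLQI show no such screener and are unaffected.

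**Conclusion.** The concern holds in a limited form. As written, Section 5.0 gives too high a Physical Function raw score to any patient who answers *No* to the screener, unless every answered item is already at its lowest category. The excess is S − 6, from 0 to 24 raw points. Change scores can take the wrong sign when the screener answer changes between visits: upward for *Yes* to *No* when S exceeds W (S unchanged), and the mirror image for *No* to *Yes*.

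This rests on reading the damaged routing line as a six-item skip after *No*, and on the lowest category as the comparator. The effect on T-scores cannot be computed because the conversion table is not in the documents; the direction carries over if T rises with the raw score. The number of patients affected is not given and is probably small. The measure is one descriptive secondary endpoint, and the safety stopping and acceptance rules do not use it. This is a minor point, worth correcting because the correction is simple.

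**What to change.** Add to Section 5.0, after checking against the cited scoring manual:

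- Physical Function items skipped because of a *No* screener answer are scored in the lowest category (1) before summing.
- Pro-rating applies only to items left blank by patients who answered *Yes*.
- The number of *No* screener answers is reported at each visit.

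If the manual prescribes something different, name that rule in Section 5.0 and give the reason for whichever is adopted, before the data are analyzed. The cost is two or three sentences. The screener is already on the form, so no new data are needed.

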# **6.0 REGULATORY CONSIDERATIONS**

# 6.1 Protection of Human Subjects

The Investigator must ensure that patients or their legally acceptable representatives are clearly and fully informed about the purpose, potential risks and other critical issues regarding clinical trials in which they volunteer to

participate. Preparation of the consent form is the responsibility of the Investigator and must include all elements required by CFR 21 Part 50.25 and the local IRB.

# 6.2 Compliance with the Protocol and Protocol Revisions

The study must be conducted as described in this approved protocol. All revisions to the protocol must be provided to the PI. The PI should not implement any deviation or change to the protocol without prior review and documented approval/favorable opinion from the IRB/IEC of an Amendment, except where necessary to eliminate an immediate hazard(s) to study patients.

The investigator must ensure that patients or their legally acceptable representatives are clearly and fully informed about the purpose, potential risks and other critical issues regarding clinical trials in which they volunteer to participate. Preparation of the consent form is the responsibility of the PI.

## 7.0 DATA HANDLING AND RECORD KEEPING

# 7.1 Confidentiality

Information about study subjects will be kept confidential and managed according to the requirements of the Health Insurance Portability and Accountability Act of 1996 (HIPAA). Those regulations require a signed subject authorization informing the subject of the following:

- What protected health information (PHI) will be collected from subjects in this study
- Who will have access to that information and why
- Who will use or disclose that information
- The rights of a research subject to revoke their authorization for use of their PHI.
- In the event that a subject revokes authorization to collect or use PHI, the
  investigator, by regulation, retains the ability to use all information
  collected prior to the revocation of subject authorization. For subjects that
  have revoked authorization to collect or use PHI, attempts should be
  made to obtain permission to collect at least vital status (i.e. that the
  subject is alive) at the end of their scheduled study period.

Confidentiality will be maintained by keeping records in secure areas in the clinic. Patient-identifiable materials, such as laboratory tests and specimens will be kept in secure areas, i.e. Nurse's station and/or freezer kept in lockable storage rooms. Computer files are accessible via password-protected computers that are kept in lockable rooms. All lab personnel that work with patient data or

samples have passed human subject protection courses, and certification of this is on file in the IRB office.

